8 STATISTICAL METHODOLOGY AND STATISTICAL ANALYSES

8.1 STATISTICAL METHODS

8.1.1 Analysis Of Categorical And Continuous Data

Categorical data will be analyzed by presenting frequency tables (absolute and relative frequencies/ adjusted and not adjusted). For continuous data the sample statistics mean, standard deviation, median, minimum and maximum, and quartiles are calculated. For incidence rates 95% confidence intervals will be presented.

Data measured several times during the study are analyzed by visit presenting absolute and relative differences to baseline for numerical data and shift tables for categorical data.

Agreement between the risks assigned to patients by the risk scores and physician's prognosis of patients risk will be measured using Cohens kappa-statistic.

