3 INTERIM ANALYSES

Two interim analyses are planned per year. A final analysis after end of study is planned with identical content. The analyses to be performed and the tables to be presented are defined in this statistical analysis plan (SAP).

Interim analyses are performed in order to get and to present early information on safety and effectiveness of a treatment with temsirolimus, sunitinib or axitinib in the usual health care setting. Interim analyses are also performed in order to get answers on new scientific questions.

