Progression free survival	EAS	1	- 1 st line patients	Kaplan-Meier estimates; Kaplan- Meier curves	 indication mRCC, GIST, MCL risk prognosis line of treatment low vs. high LDH response to prior therapy age groups (≤65 yrs; > 65 yrs) histology (clear cell vs. non-clear cell) 	
Response to therapy	EAS	1	- risk prognosis	Frequency table	None	Excluded
Physician's global assessment	EAS	1	None	Sample statistics by visit	Risk prognosis	Excluded
Karnofsky Performance Index	EAS	4, 5	None	Sample statistics by visit	Only GIST, mRCC	Excluded
ECOG Performance Score	EAS	4, 5	- risk prognosis	Frequency table; shift tables	Only MCL	Excluded
FKSI-15	EAS	6	- risk prognosis	Sample statistics	Only mRCC	Excluded
EQ-5D	EAS	6	- risk prognosis	Frequency table for EQ-5D, Sample statistics for EQ-5D-VAS; EQ-5D-TTO	Only mRCC	Excluded

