2.5-1	Course of ECOG performance status	MCL	EAS	Frequency table by time windows and for the last documented visit, shift table for differences to baseline (in total and by patient risk groups)
2.5-2	Course of B-symptoms	MCL	EAS	Frequency table by time windows and for the last documented visit
2.6	FKSI-15: Course			
2.6-1	Course of FKSI-15 score	mRCC	EAS Sequence analysis	Sample statistics by time windows and for the last documented visit and absolute and relative change to baseline.
2.6-2	Course of FKSI-DRS score	mRCC	EAS Sequence analysis	Sample statistics by time windows and for the last documented visit and absolute and relative change to baseline.
2.6-3	Course of FKSI domains	mRCC	EAS Sequence analysis	Sample statistics by time windows and for the last documented visit and absolute and relative change to baseline.
2.7	EQ-5D: Course			
2.7-1	Course of EQ-5D: domains	mRCC	EAS Sequence analysis	Frequency tables by time window and for the last documented visit and shift tables to baseline
2.7-2	Course of EQ-5D-VAS	mRCC	EAS Sequence analysis	Sample statistics by time windows and for the last documented visit and absolute and relative change to baseline.

Table No.	Title	Treatment/ Indication	Analysis set	Description
2.7-3	Course of EQ-5D: TTO	mRCC	EAS Sequence analysis	Sample statistics by time windows and for the last documented visit and absolute and relative change to baseline.
3	Safety			
3.1	Display of adverse events (AE)			
3.1-1.1	Summary of adverse events	All	Safety	No. / % of patients - at risk - with AE - with drug related AE - with AE related to Pfizer treatment - with AE related to interim treatment - with SAE - with drug related SAE - with SAE related to Pfizer treatment - with SAE related to Pfizer treatment - with SAE related to interim treatment - with AE leading to permanent discontinuation of Torisel®/ Sutent® / Inlyta® - with drug related AE leading to permanent discontinuation of Torisel®/ Sutent® / Inlyta® - with SAE leading to permanent discontinuation of Torisel®/ Sutent® / Inlyta® - with drug related SAE leading to permanent discontinuation of Torisel®/ Sutent® / Inlyta® - with drug related SAE leading to permanent discontinuation of Torisel®/ Sutent® / Inlyta® - Death No. / % of AE - all AE - drug related - related to Pfizer treatment - related to interim treatment - SAE - drug related SAE - SAE related to Pfizer treatment - SAE related to interim treatment

Table No.	Title	Treatment/ Indication	Analysis set	Description

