				.1 total .2 by treatment sequence .3 by line
3.1-1.2	Summary of adverse events by concomitant CYP3A4 inducing or inhibiting medications	Torisel® mRCC / MCL	Safety	repeat table 3.1-1.1 by subgroups according to CYP3A4 inducing or inhibiting medication (if number of patients with these medications is sufficiently large
3.1-2	All adverse events (by patients)	All	Safety	Incidence rates overall and for Primary System Organ Classes (PSOC) and preferred terms of MedDRA (non-serious/serious as columns) 1 total 2 by treatment sequence 3 by line
3.1-3	AE by severity (NCI-CTC grade)	All	Safety	Incidence rates overall and for PSOC and preferred terms of MedDRA severity: max. NCI-CTC grade within patient, PSOC, preferred term resp.(non-serious/serious as columns)
3.1-4	AE with relationship to study drug	All	Safety	Incidence rates overall and for PSOC and preferred terms of MedDRA (non-serious/serious as columns)
3.1-5	AE with action taken "Study medication permanently discontinued"	All	Safety	Incidence rates overall and for PSOC and preferred terms of MedDRA (non-serious/serious as columns)
3.1-6	AE by outcome (event basis)	All	Safety	Number of events overall and for PSOC and preferred terms of MedDRA
3.1-7	Treatment emergent AE: action taken (event basis)	All	Safety	Number of events overall and for PSOC and preferred terms of MedDRA
3.2	Deaths, other serious and significant adverse events			
3.2-1.1	Listing of deaths	All	Safety	Sorted by patient
3.2-1.2	Reason for death	All	Safety	Frequency table
3.2-1.3	Listing of serious adverse events (SAE, except deaths)	All	Safety	Sorted by patient

Table No.	Title	Treatment/ Indication	Analysis set	Description
3.2-1.4	Listing of SAE with outcome study treatment permanently discontinued	All	Safety	Sorted by patient
3.3	Laboratory values			
3.3-1	Hematology			
3.3-1	Laboratory values: hematology – study course	All	Safety	.x per parameter Sample statistics by visit, including difference and relative changes to baseline
3.3-2	Clinical chemistry			
3.3-2	Laboratory values: clinical chemistry- study course	All	Safety	.x per parameter Sample statistics by visit, including difference and relative changes to baseline
3.4	Global tolerability assessment			
3.4	Physician's global tolerability assessment	All	Safety	Frequency table by time windows and for the last documented visit
3.5	Vital signs, ECG, echocardiography and pain			
3.5-1	Course of blood pressure	mRCC	Safety	Sample statistics by time windows

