Treatment duration (weeks) = (date of death or date of drop-out or date of end of treatment with Torisel®/ Sutent® - date of first infusion within the registry + 1)/365.25 * 52.

Therapy line

for patients with mRCC:

- Splitted therapy (due to coding) was only counted as one therapy line.
- All medication with an identical start date was counted as one therapy line.
- Interferons, interleukins and immunochemotherapies were summarized as "cytokines".
- Ongoing treatment with the medication documented was not counted as line.
- Bisphosphonates and other supplementary treatment will not be considered. for patients with MCL:
 - Splitted therapy (due to coding) was only counted as one therapy line.
 - All medication with an identical start date was counted as one therapy line.
 - Rituximab maintenance therapy and stem cell transplantation, both connected with previous immunochemotherapy (ATC L01 Antineoplastic agents and L03 Immunostimulants), were not counted as line.

Rituximub were counted as maintenance therapy, if

- physician's comment contained free text / phrases like "Erhaltung", "Erhalt", "Maintenance" or
- (last therapy prior to Rituximab resulted in remission (CR, PR or MR) and
- Rituximab was started directly after the last therapy (at most one therapy free month was tolerable).)

FKSI-15

For calculation of the FKSI-15 score documented values for questions 1-6, 8,9, 11, 12 and 14 will be reversed by subtracting the documented value from 4. All original scores (for questions 7, 10, 13 and 15) and all reversed scores will be summed, multiplied by 15 and devided by the number of answered questions resulting in a score within a range from 0 to 60. The FKSI-15 score cannot be determined if more than 7 questions are not answered.

FKSI-DRS score will be calculated like the FKSI-15 score considering only questions 1, 3, 4, 5, 6, 8, 11, 12 and 14 (multiply by 9). FKSI-DRS cannot be determined if more than 4 questions are not answered.

The 4 domains of FKSI-15 will be calculated like the FKSI-15 score. The following tables shows domains and related questions, multiplyer and maximal number of unanswered questions in order to give a valid score.

Domain	Questions	Multiplyer	Maximal number of unanswered questions
Signs and symptoms	1, 2, 3, 4, 5, 6, 12, 13	8	4
Respiratory symptoms	8, 11	2	1
Quality of life	7, 10, 13, 15	4	2
Emotional symptom	9	1	0

EQ-5D (TTO)

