EQ-5D-TTO will be calculated from EQ-5D raw values according to the following formula (Greiner, W. et al. 2005):

EQ-5D-TTO = 0.999

- 0.099 * (1*Subject has some problems with walking around + 2 * Subject cannot walk around)

- 0.087 * (1*Subject has some problems with self-care + 2 * Subject has extreme problems with self-care)

- 0.112 * (1*Subject states moderate pain or discomfort + 2 * Subject has extreme pain or discomfort)

- 0.129 * (Subject cannot walk around)

- 0.091 * (Subject has extreme pain or discomfort)

- 0.065 * (Subject is extremely anxious or depressive)

- 0.323 * (Subject states major problems in at least one dimension).

EQ-5D-TTO-values range from -0.205 to 0.999.

Laboratory values

Additional queries were written in the following cases:

- calcium > 10 mmol/L
- albumin > 100 g/L
- hemoglobin > 20 g/dL
- LDH < 80 U/L or > 1000 U/L
- albumin in % of total protein.

Laboratory values were set to "missing" if the documented values were outside the ranges given in the following table:

Laboratory parameter	Lower plausibility range	Upper plausibility range
Neutrophils	6%	100%
Lymphocytes	2.5%	85%
Monocytes	-	26%
Eosinophils	-	16%
Basophils	-	5%
Leukocytes	-	28 G/L
Platelets	-	1000 G/L
Hemoglobin*	-	20 g/dL
Creatinine	-	12 mg/dL
Calcium*	-	10 mmol/L
Sodium	-	320 mmol/L
Potassium	-	15 mmol/L
Phosphate	-	4 mmol/L
Magnesium	-	7 mmol/L
ALT (GPT)	1 U/L	1400 U/L

Laboratory parameter	Lower plausibility range	Upper plausibility range
AST (GOT)	1 U/L	1400 U/L
Gamma-GT	1 U/L	1400 U/L
Alkaline Phosphatase	1 U/L	5100 U/L
Total bilirubin	-	25 mg/dL
Albumin	-	100 g/L
LDH*	80 U/L	1000 U/L
Cholesterol	-	26 mmol/L
Triglycerides	-	35 mmol/L
HbA1c	1%	10%
Glucose	-	_**
TSH	-	21 mU/L
beta-2 Microglobulin	-	-

^{*:} Risk factors according to Motzer score will be set prior to check on plausibility.

CYP3A4-inducing and inhibiting substances

A combination of Torisel® and CYP3A4 influencing substances should be handled carefully. Thus documented concomitant medication will be checked manually for CYP3A4 inducing and inhibiting substances by the medical expert.

If the number of patients who received either CYP3A4 inducing or inhibiting substances is sufficiently large, parts of the safety analysis will be repeated for those subgroups.

Comorbidities

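### Relative change from baseline is planned for EQ-5D-TTO, which can be negative; divided by a signed baseline, every change from a negative baseline takes the wrong sign

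*SAP*

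**What the plan says.** SAP 8.1.1 sets the general rule for data measured several times: analysis by visit, "presenting absolute and relative differences to baseline for numerical data". The same section lists the sample statistics as mean, standard deviation, median, minimum, maximum and quartiles.

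SAP section 9 applies the rule to the index explicitly. Table 2.7-3, "Course of EQ-5D: TTO", is described as "Sample statistics by time windows and for the last documented visit and absolute and relative change to baseline". It is planned for mRCC patients in the effectiveness set and again in the sequence analyses. The EQ-5D row of SAP 8.2.3 also plans "Sample statistics for EQ-5D-VAS; EQ-5D-TTO", with risk prognosis as a subgroup.

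SAP Appendix 1 (A1.3) gives the scoring formula and states: "EQ-5D-TTO-values range from -0.205 to 0.999".

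Neither document defines relative change, exempts EQ-5D-TTO from it, or says what to do when a baseline is negative, zero or close to zero.

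**The concern.** A percentage change needs a scale with a true zero and positive values. EQ-5D-TTO, by the SAP's own range, passes through zero. With the usual definition the denominator is negative for the worst health states, so an improvement is reported as a percentage fall and a deterioration as a percentage rise. Near zero the percentage becomes extreme in either direction.

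These values are not dropped. No EQ-5D-TTO state equals exactly 0, so each quotient can be computed and enters the mean and standard deviation. The more such patients improve, the further they pull the mean relative change down. Table 2.7-3 could therefore show an absolute and a relative change of opposite sign, with no rule to tell the reader which to believe. Quality of life in advanced RCC is a listed objective in both documents, and the protocol plans publication of the final results.

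**Working it through.** **Inputs.** The formula and range are in SAP Appendix 1, EQ-5D (TTO). The plan for relative change is in SAP 8.1.1 and Table 2.7-3. Assumption, because the SAP gives no formula: relative change = (follow-up - baseline) / baseline. States are written as levels 1 to 3 of mobility, self-care, usual activities, pain and anxiety/depression, in that order.

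**1. Reproduce the stated range.** Best state: 0.999. Worst state, 33333: 0.999 - 0.198 - 0.174 - 0.224 - 0.129 - 0.091 - 0.065 - 0.323 = -0.205. Both ends agree with the SAP.

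**2. Count the negative states.** There are 3^5 = 243 states. The formula gives 24 negative values: -0.205 (3 states), -0.140 (6), -0.118 (3), -0.053 (6), -0.031 (3) and -0.002 (3). None is 0. All 24 combine the worst mobility level with moderate or extreme pain, plus a self-care problem or extreme anxiety. The three moderate-pain states (-0.002) need the worst level of both self-care and anxiety. Another 24 states lie between 0.023 and 0.088. These are counts of states, not of patients.

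**3. Check the direction.** Over all ordered pairs of states with a negative baseline and a non-zero change, 5,724 of 5,724 have a relative change of opposite sign to the absolute change. For positive baselines, 0 of 53,217 pairs do.
- Improvement: (0.701 + 0.205) / (-0.205) = 0.906 / (-0.205) = -442%.
- Deterioration: (-0.205 + 0.053) / (-0.053) = -0.152 / (-0.053) = +287%.

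**4. Try the absolute baseline as denominator.** The signs become right, but -0.002 to 0.701 is 0.703 / 0.002 = +35,150%. Small positive baselines have the same problem: 0.023 to 0.701 is 0.678 / 0.023 = +2,948%.

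**5. Effect on the group mean (illustration).** Assume that a share of patients starts at -0.205 and that all others move from 0.701 (state 22222) to 0.800 (state 12222). Their relative change is o = 0.099 / 0.701 = 14.1% (unrounded in the table). For a patient starting at -0.205, r is the relative change.
- Break-even share, above which the mean relative change is negative: o / (o + |r|).
- With a 5% share: mean relative = 0.05 × r + 0.95 × o; mean absolute = 0.05 × (follow-up + 0.205) + 0.95 × 0.099.

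| Follow-up from -0.205 | r | Break-even share | Mean absolute, 5% share | Mean relative, 5% share |
|---|---|---|---|---|
| -0.140 | -31.7% | 30.8% | +0.097 | +11.8% |
| -0.118 | -42.4% | 25.0% | +0.098 | +11.3% |
| -0.002 | -99.0% | 12.5% | +0.104 | +8.5% |
| 0.023 | -111.2% | 11.3% | +0.105 | +7.9% |
| 0.226 | -210.2% | 6.3% | +0.116 | +2.9% |
| 0.701 | -442.0% | 3.1% | +0.139 | -8.7% |

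Down the last two columns, absolute change rises while relative change falls. At the break-even shares the mean absolute change is still +0.089 to +0.124.

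**6. Sensitivity to the other patients.** If the others average +5%, the break-even share runs from 0.05 / (0.05 + 4.420) = 1.1% to 0.05 / (0.05 + 0.317) = 13.6%. At +30% it runs from 0.30 / 4.720 = 6.4% to 0.30 / 0.617 = 48.6%.

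**7. Zero baselines elsewhere (minor).** FKSI-15 is scored "resulting in a score within a range from 0 to 60". Its emotional domain (one item, 0 to 4) and respiratory domain (two items, 0 to 8) reach 0 most easily. Tables 3.3-1 and 3.3-2 plan "Sample statistics by visit, including difference and relative changes to baseline", and Appendix 1 sets no lower plausibility limit for basophils or eosinophils. At a zero baseline the quotient is undefined, and 8.1.1 has no rule for it.

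**The case against.** The case on the other side is about weight. The registry is descriptive, with no hypotheses or decision rules, and the correctly signed absolute change is in the same table. Median and quartiles are also planned. In the 5% illustration both quartiles and the median of relative change stay at +14.1%, so only the mean, standard deviation and minimum are distorted. The shares are assumed, and they place patients in the very worst state. The documents give no baseline distribution, so the real effect could be nil. The sign reversal depends on a signed denominator that the SAP does not specify. A zero baseline would in practice drop out, because SAP 8.2.3 excludes missing data for these variables.

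Most of this stands, and it limits the impact. It does not make the column valid. The alternative denominator trades wrong signs for extreme percentages, and the SAP leaves the choice open. The mean is a planned statistic, and the table is repeated by time window and for seven sequence groups, some of which may be small. In a group of 20, one patient is 5%. The zero-baseline point is indeed minor; a rule there mainly makes the reduced number of patients visible.

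**Conclusion.** The concern holds. As written, Table 2.7-3 yields a mean and standard deviation of relative change that are wrongly signed or uninterpretable whenever a negative or near-zero baseline occurs. The reversal for every changed value from a negative baseline rests on the signed-denominator assumption; the instability near zero holds under either definition.

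The size in this registry cannot be stated, because the documents do not say how many patients start in one of the 24 negative states. In the scenarios, the share at -0.205 needed to turn the mean relative change negative is 3.1% to 30.8%, or 1.1% to 48.6% across the other assumptions about the remaining patients. Distortion without reversal occurs at smaller shares. No decision rests on this column, so this is a correction that should be made, not one on which the study's conclusions depend.

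**What to change.** Delete relative change from Table 2.7-3 and report absolute change only. Limiting the column to positive baselines would not be enough, because the small positive states also give extreme percentages and the patients in the worst health would be left out.

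Add to SAP 8.1.1:

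> Relative differences to baseline are not presented for EQ-5D-TTO. For other numerical variables the relative difference is (value - baseline)/baseline. It is not calculated when the baseline is 0, and its n is shown beside the n of the absolute difference.

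Relative change stays in the FKSI, EQ-5D-VAS, Karnofsky and laboratory tables.

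The cost is one table shell and three sentences, plus an added n in the tables that keep relative change, including their repeats for the sequence groups. No new data are needed, and absolute change is already planned. The drawback is that the EQ-5D-TTO table will no longer match earlier interim outputs, although SAP section 3 says "A final analysis after end of study is planned with identical content". The change should therefore be recorded in the SAP's list of amendments.

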8.1.2 Analysis Of Survival Data

OS, PFS and treatment duration will be analyzed using Kaplan-Meier plots. Median, 25% and 75% survival times with confidence intervals for OS and PFS will be presented. For stratification according to physician's prognosis and for risk groups according to Motzer score/MIPI/Fletcher risk table, log-rank tests will be performed.

8.2 STATISTICAL ANALYSES

8.2.1 Summary of Efficacy/ Effectiveness Analyses

Not applicable

8.2.2 Safety Analyses

Adverse events will be analyzed giving absolute and relative frequencies in total and by MedDRA system organ classes and preferred term. Serious adverse events will be analyzed separately in the same manner.

Adverse events will presented within each treatment (temsirolimus, sunitinib, axitinib) and for all non-Pfizer treatments in total and by treatment.

Additionally the absolute and relative frequency of patients with premature discontinuation will be presented in total and by reason for premature discontinuation.

Prior and concomitant medication will be presented showing frequency tables.

Laboratory results and ECG results will be presented by visit.

Physician's assessment of tolerability will be analyzed presenting sample statistics.

8.2.3 **Summary of Analyses**

Outcome	Analysis Set	Supports Protocol Objective Number	Subgroups	Statistical Method	Covariates/ Strata	Missing Data
Demographic characteristics: age, height, weight, BMI, sex	Safety, EAS	4	None	Sample statistics	None	Excluded
Incidence of treatment- emergent adverse events	Safety	3	Patients receiving CYP3A4 inducing concomitant medication (only patients treated with temsirolimus) Patients receiving CYP3A4 inhibiting concomitant medication (only patients treated with temsirolimus)	Rate by SOC and PT	Non-serious AE, serious AE	Excluded
Discontinuations due to AE	Safety	3	None	Rate by SOC and PT	None	Excluded
Discontinuation from Study	Safety	3	None	Rate for reason for discontinuation	None	Excluded
Serious Adverse Events	Safety	3	None	Rate by SOC and PT	None	Excluded
Deaths	Safety	3	None	Rates for reason for deathListing of deaths	None	Excluded
Laboratory values	Safey	3	None	Sample statistics by parameter and visit	None	Excluded

Outcome	Analysis Set	Supports Protocol Objective Number	Subgroups	Statistical Method	Covariates/ Strata	Missing Data
Global tolerability assessment	Safety	2	None	Frequency table	None	Excluded
Overall survival	EAS	1	- 1 st line patients	Kaplan-Meier estimates; Kaplan- Meier curves; Log-rank test	 indication mRCC, GIST, MCL risk prognosis line of treatment low vs. high LDH response to prior therapy age groups (≤65 yrs; > 65 yrs) 	
Progression free survival	EAS	1	- 1 st line patients	Kaplan-Meier estimates; Kaplan- Meier curves	 indication mRCC, GIST, MCL risk prognosis line of treatment low vs. high LDH response to prior therapy age groups (≤65 yrs; > 65 yrs) histology (clear cell vs. non-clear cell) 	
Response to therapy	EAS	1	- risk prognosis	Frequency table	None	Excluded
Physician's global assessment	EAS	1	None	Sample statistics by visit	Risk prognosis	Excluded
Karnofsky Performance Index	EAS	4, 5	None	Sample statistics by visit	Only GIST, mRCC	Excluded
ECOG Performance Score	EAS	4, 5	- risk prognosis	Frequency table; shift tables	Only MCL	Excluded
FKSI-15	EAS	6	- risk prognosis	Sample statistics	Only mRCC	Excluded
EQ-5D	EAS	6	- risk prognosis	Frequency table for EQ-5D, Sample statistics for EQ-5D-VAS; EQ-5D-TTO	Only mRCC	Excluded

